#### 3.5.3.3.2 Male Endpoints

I. Persistent infection (with duration of 6 months):

This endpoint is defined to have occurred if a subject who, after completion of the Month 7 visit, is positive for the same HPV type by the HPV 6/11/16/18/31/33/45/52/58 PCR assay to at least 1 common gene in 2 or more consecutive anogenital swab or biopsy obtained at two or more consecutive visits 6 months (± 1 month) or longer.

Persistent infection is defined based on the protocol visit intervals. Scheduled visits for the collection of swabs are at 6-monthly intervals, so most cases of persistent infection will be based on consecutive specimens obtained 6 months apart; however, due to protocol-allowable deviations for scheduled visit intervals, the minimum length of time between samples for a subject to be counted as a case of persistent infection will be 4 months.

If a subject has 2 consecutive samples that are PCR positive to at least one common gene for the same HPV type and at least one of the samples is a biopsy or definitive therapy sample showing pathologic evidence of HPV disease, then the subject will be considered a case of persistent infection without regard to the length of time between the samples.

II. External genital warts, PIN, or penile/perineal/perianal cancer related to HPV 6, 11, 16, 18, 31, 33, 45, 52 or 58:

A subject will be considered to have this endpoint if he has the following:

• Pathology panel consensus diagnosis of genital warts, PIN 1, PIN 2, PIN 3, penile, perineal, or perianal cancer, AND

74

• Detection of HPV 6, 11, 16, 18, 31, 33, 45, 52, or 58 DNA by Thinsection PCR in an adjacent section of the same tissue block.

The composite effectiveness endpoints for each gender include all of the gender-specific endpoints listed above. The incidence of each individual component will be summarized, as will the incidence of the composite endpoints for each gender. Endpoints related to non-vaccine types (i.e., HPV 35, 39, 51, 56, and 59), for the exploratory effectiveness analyses, are defined in the same way as the vaccine-type endpoints.

If a subject has experienced one or more of the components of the respective endpoint, he or she will be counted once in the summary of incidence rates of the composite endpoint, at the time of detection of the first endpoint for which the subject meets the case criteria. For example, if a subject has AIS related to HPV 16 and CIN related to HPV 18, she will be counted only once in the summary of the composite endpoint of HPV 6, 11, 16, 18, 31, 33, 45, 52, or 58 persistent infection, external genital warts, VIN, VaIN, AIS, or CIN. For summaries of individual components of the composite endpoint, a subject may be counted as a case at most once in each applicable category, but may appear in multiple sub-categories. In the example above, the subject would be counted as a case in a summary of HPV 16-related disease and also in a summary of HPV-18 related disease.

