#### 2.1.2 Secondary Objectives

- (1) Co-Secondary Objective: To estimate the long-term effectiveness of 9-valent HPV L1 VLP vaccine, when administered to 9- to 15-year-old girls, with respect to the combined incidence of persistent HPV 6, 11, 16, 18, 31, 33, 45, 52, and 58 infection for a duration of 6 months (within ± 1 month windows) or longer and HPV 6, 11, 16, 18, 31, 33, 45, 52, and 58-related Cervical Intraepithelial Neoplasia (CIN), Adenocarcinoma In Situ (AIS), Vulvar Intraepithelial Neoplasia (VIN), Vaginal Intraepithelial Neoplasia (VaIN), genital warts, and cervical/vaginal/vulvar cancer.
- (2) Co-Secondary Objective: To estimate the long-term effectiveness of 9-valent HPV L1 VLP vaccine, when administered to 9- to 15-year-old boys, with respect to the combined incidence of persistent HPV 6, 11, 16, 18, 31, 33, 45, 52, and 58 infection for a duration of 6 months (within ± 1 month windows) or longer and HPV 6, 11, 16, 18, 31, 33, 45, 52, and 58-related Penile Intraepithelial Neoplasia (PIN), genital warts, and penile/perineal/perianal cancer.

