#### 3.1.2 Rationale for This Study

#### 3.1.2.1 Rationale for Assessment of Long Term Effectiveness

Protocol V503-002, a 12-month immunogenicity and safety study of V503 in preadolescent and adolescent girls and boys, showed that V503 is highly immunogenic and generally well-tolerated in the study population. Girls and boys enrolled in V503-002 are being followed for 24 additional months under Study Extension V503-002-10, to assess persistence of antibody responses and long term safety.

Taken together, the Protocol V503-002 base study and V503-002-10 study extension will provide immunogenicity and safety data through approximately 36 months of study follow-up. Efficacy data were not collected in V503-002 and V503-002-10 because evaluation of sexual history and gynecological/genital examination is limited in young adolescents by social, cultural, and legal constraints. Nonetheless, data on the long term immunogenicity, safety, and effectiveness of V503 administered to preadolescent and adolescent girls and boys will support ongoing use of the vaccine in this important target population.

In the current protocol, immunogenicity and safety information will be collected for all subjects, and effectiveness endpoints will be assessed in subjects who have reached 16 years of age. Collection of efficacy data will be dependent on age and gender. Data permitting, the protocol will evaluate the long term effectiveness of V503 in preventing HPV persistent infection as well as HPV disease caused by HPV types targeted by V503, including external genital warts in both genders; cervical, vulvar, and vaginal intraepithelial neoplasia, and associated cancers in female subjects; penile, perineal, and perianal intraepithelial neoplasia, and associated cancers in male subjects.

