# 3.2.2.14.3 External Genital Swabs (Male Subjects ≥16 Years of Age)

One (1) penile/glans swab, 1 scrotal swab, and 1 perineal/perianal swab for HPV PCR assay will be collected at each study visit following completion of the external genital examination.

For collection of swabs, the study site must adhere to the procedures described in this protocol, must follow instructions provided by the SPONSOR/Central Laboratory, and must use the materials provided by the SPONSOR/Central Laboratory (see Section 3.2.4).

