### 3.2.3.1.2 External Genital Lesion and Vaginal Lesion Diagnosis and Follow-Up

External genital lesions or vaginal lesions may be identified during a scheduled visit exam, Pap test, colposcopic examination, or at any other time during the study. For the purposes of this study, lesions that require access via the introitus (with the exception of the cervix, which is considered a separate location) are to be defined as vaginal lesions. Lesions that are external to the introitus are to be defined as external genital lesions. To classify the location of external genital lesions, the external genital area will be further divided into the following 4 regions:

- periurethral (includes the clitoris)
- perineal
- perianal
- vulvar (includes all areas other than the periurethral, perineal or perianal regions)

It is important to make an accurate evaluation of any identified external genital lesions. The practitioner must classify a lesion as condyloma acuminata, other HPV-related lesion (e.g., a flat wart, a papular wart, a keratotic wart, VIN, Bowenoid papulosis, Bowen's disease) or a non HPV-related lesion. If lesions are identified, they must be documented on the appropriate eCRF.

External genital lesions suspected to be possibly, probably, or definitely HPV-related (i.e., clinical impression of condyloma acuminata or other HPV-related lesion) or of unknown etiology are to be biopsied. Separate biopsies should be performed if external genital lesions are at different locations (periurethral, perineal, perianal, or vulvar region) or if more than one external genital lesion is at the same location and has a different morphology. An additional external genital lesion biopsy should be obtained if a new HPV-related lesion (or lesion of unknown etiology) appears and is of differing morphology and/or differing location from the initial lesion(s). A recurrent lesion should not be biopsied. A recurrent external genital lesion is defined as a lesion that has both of the following characteristics: (1) appears within 2 months of the complete resolution of an initial lesion(s) and (2) has the same location and a similar morphology as the initial lesion(s). If an HPV-related lesion or a lesion of unknown etiology appears after 2 months of complete resolution of the initial lesion(s), a biopsy of the lesion should be taken.

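### Perineal and perianal intraepithelial neoplasia is in the planned disease summaries but has no case rule in males; in females neither neoplasia nor cancer at these sites has one

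*Combined protocol and SAP*

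**What the plan says.** **Male rule.** Endpoint II in Section 3.5.3.3.2 needs a "Pathology panel consensus diagnosis of genital warts, PIN 1, PIN 2, PIN 3, penile, perineal, or perianal cancer", together with a vaccine HPV type found by Thinsection PCR in an adjacent section of the same block. Co-secondary objective 2 (Section 2.1.2) has the same scope: "Penile Intraepithelial Neoplasia (PIN), genital warts, and penile/perineal/perianal cancer". It spells PIN out as penile, so the abbreviation does not reach the perineum or perianal skin.

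**Stated scope.** Section 3.1.2.1 divides the sites by sex, data permitting: "cervical, vulvar, and vaginal intraepithelial neoplasia, and associated cancers in female subjects", and "penile, perineal, and perianal intraepithelial neoplasia, and associated cancers in male subjects". Sections 2.7.2, 2.7.5, 3.5.5.3 and 3.5.9 plan summaries, separately for males and females, from one pooled list that includes perineal and perianal intraepithelial preinvasive and invasive disease. Section 1.3 carries the same list.

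**Female rule.** Section 3.5.3.3.1 counts genital warts, VIN, VaIN, CIN, AIS, and vulvar, vaginal and cervical cancer. Section 3.2.3.1.2 treats perineal and perianal as regions of their own; the remaining region is "vulvar (includes all areas other than the periurethral, perineal or perianal regions").

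**Reporting.** "The incidence of each individual component will be summarized, as will the incidence of the composite endpoints for each gender". Section 3.5 says that no separate SAP will be issued.

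**The concern.** The extension tests no hypothesis, so its effectiveness result is a set of counts and rates, and the case definitions determine those counts. As written, a male with a perineal or perianal precancer confirmed by the panel and positive for a vaccine type meets no disease rule. A wart or a cancer at the same place would count. The plan gives no reason for leaving out the stage between them.

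If such a lesion occurs, someone must decide with the data in hand whether it is PIN, something else, or not a case. The study is open-label and has no separate SAP to settle the matter. Any omission lowers the disease rate, which favours the vaccine. The gap also passes to the exploratory analyses of HPV 35, 39, 51, 56 and 59, because Section 3.5.3.3.2 defines those endpoints in the same way.

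**Working it through.** The plan gives no figure to reproduce, so the check compares lists.

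**1. Sites in the summaries against sites with a case rule**

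| Perineal/perianal category | In pooled summary list | Male rule (3.5.3.3.2) | Female rule (3.5.3.3.1) |
|---|---|---|---|
| Warts | yes, under external genital lesions | yes | yes, as external genital warts |
| Intraepithelial neoplasia | yes | **no** | **no** |
| Cancer | yes | yes | **no** |

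For males, Section 3.1.2.1 names intraepithelial neoplasia at three sites and the rule defines it at one; cancer is defined at all three. For females the gap is wider, because cancer at these sites has no rule either.

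**2. Can such lesions reach the database?** Yes.
- Males: the perineal and perianal area is the posterior biopsy region (Sections 3.2.3.2.1 and 3.2.4.3.4). Biopsies are read by the panel and typed whatever the histology.
- Females: lesions in these regions that are HPV-suspect or of unknown cause are biopsied (Section 3.2.3.1.2). All tissue is panel-read and typed (Section 3.2.3.1.3).

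**3. Does the male composite lose the subject?** Usually not, for two reasons.
- From age 16, "1 perineal/perianal swab for HPV PCR assay will be collected at each study visit". A male already 16 at Month 42 has up to (126 − 42)/6 + 1 = 15 scheduled visits.
- Suppose two consecutive samples are positive for the same type and a common gene, and one is a biopsy showing HPV disease: "then the subject will be considered a case of persistent infection without regard to the length of time between the samples".

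The composite loses the subject only if no consecutive sample matches. The disease component loses the subject in every case.

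**4. Size for the male disease component**

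The documents give neither an expected number of these lesions nor male person-years (PY). The PY values and case counts below are assumptions.

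- Rate per 100 PY = 100 × k / PY, where k is the number of cases, so each omitted subject lowers it by 100/PY.
- Exact Poisson 95% limits on the count: lower χ²(0.025; 2k)/2 (0 when k = 0), upper χ²(0.975; 2k + 2)/2. Results: k = 0: 0 to 3.69; k = 1: 0.03 to 5.57; k = 2: 0.24 to 7.22; k = 3: 0.62 to 8.77.

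| Male PY (assumed) | Per omitted subject | 2 cases counted | 3 cases counted |
|---|---|---|---|
| 500 | 0.20 | 0.40 (0.05–1.44) | 0.60 (0.12–1.75) |
| 1000 | 0.10 | 0.20 (0.02–0.72) | 0.30 (0.06–0.88) |
| 2000 | 0.05 | 0.10 (0.01–0.36) | 0.15 (0.03–0.44) |
| 4000 | 0.025 | 0.05 (0.01–0.18) | 0.075 (0.02–0.22) |

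If the only case is the omitted one, the upper limit at 2000 PY is 0.18 (3.69/2000 × 100) instead of 0.28 (5.57/2000 × 100). The intervals overlap widely in every row. The table shows scale; it does not show that any such lesion is expected.

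**The case against.** **The objective and the rule agree.** Every disease in co-secondary objective 2 has a case definition. The conflict is with a rationale paragraph qualified by data permitting and with a narrative list pooled across the sexes. This stands, and it limits the claim: nothing is undercounted relative to objective 2. But the same list is the stated content of the planned summaries in four sections, and a category planned for reporting needs a rule.

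**Persistent infection picks these subjects up.** For the composite this is largely right. It does not repair the disease component, which is reported separately and would lack the subject.

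**The panel may label such lesions PIN or VIN.** Section 3.3.3 mentions an approved guideline on the panel process, but its content is not shown. The mismatch in the text is certain; the loss of actual cases is not.

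**No rule fills the listed category.** A reader might infer this, but for males it goes too far, because perineal and perianal cancer is defined. Only the preinvasive part is missing.

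**The sites could be removed from the female tables, since the rationale assigns them to males.** A reader might infer this too. The rationale does not say that female disease there is out of scope, and female tissue from these regions is biopsied, read and typed as well. Deletion would hide the wider of the two gaps.

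**Conclusion.** The mismatch holds on the text. Male preinvasive disease at the perineum and perianal area is within the stated scope and the planned summaries but has no case rule. Female disease at these sites has no rule for neoplasia or for cancer.

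Measured against Section 3.1.2.1 and the summaries, the male disease component can only be understated. Its size is unknown: 0.20 to 0.025 per 100 person-years per omitted subject over an assumed 500 to 4000 male person-years. The small effect on the composite rests on most affected subjects having a matching consecutive sample. The swab schedule makes that likely, but the documents do not quantify it.

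A reader might infer that male effectiveness is materially overstated. The documents do not support that: they give no lesion count or person-years, the illustrative intervals overlap widely, and no hypothesis, power or multiplicity question is involved. Severity is minor.

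**What to change.** Before the Month 72 database freeze:

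1. **Males.** Add perineal and perianal intraepithelial neoplasia to endpoint II in Section 3.5.3.3.2, with grades listed as for PIN 1 to 3 and the same Thinsection PCR condition, and to co-secondary objective 2. The rule then matches Section 3.1.2.1 and the summaries. Narrowing the rationale and summaries would also remove the mismatch. Adding the category is preferable because the rule already counts warts and cancer at these sites.
2. **Females.** Keep the sites in the summaries. Reconcile Section 3.5.3.3.1 and co-secondary objective 1 with the list in Sections 1.3, 2.7.2, 2.7.5, 3.5.5.3 and 3.5.9, so that every listed site has a case rule for both preinvasive and invasive disease.

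**Cost.** Amendment text for two objectives and two case definitions. No new visit, specimen or assay is needed, because the tissue is already collected, read and typed. Reported rates may be slightly higher.

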## 3.5.4 Analysis Populations

## 3.5.4.1 Immunogenicity Analysis Populations

The primary approach to the analysis of immunogenicity will be per-protocol, including subjects without major protocol violations who are seronegative to the respective HPV type pre-vaccination.

## Per Protocol Immunogenicity (PPI) Population

The PPI population will serve as the primary population for the analysis of immune response to each of the 9 HPV types (6, 11, 16, 18, 31, 33, 45, 52, and 58). To be included in this population, subjects must:

- (1) Have received all 3 vaccinations with the correct dose of the correct clinical material, and each vaccination visit must occur within acceptable day ranges (See Table 3-5 for acceptable day ranges for vaccination visits).
- (2) Be seronegative by cLIA to the appropriate HPV type at Day 1 (See Table 3-6 for acceptable day ranges for serum).
- (3) Have no other protocol violations that could interfere with the evaluation of subject's immune response to the study vaccine. Specifically, at base study Day 1, satisfied the inclusion criterion 5 (i.e., "Subject must not yet have had coitarche

and does not plan on becoming sexually active during the Day 1 through Month 7 period.") specified in Section 2.2 of the protocol of the base study (i.e., Protocol V503-002-00).

To be included in the PPI population for HPV 6 and 11, subjects must be seronegative by cLIA to both HPV 6 and 11 at Day 1. To be included in the PPI population for any other vaccine HPV type, subjects need to be seronegative by cLIA at Day 1 only for the HPV type being analyzed.

75

The final determination on protocol violations, and thereby the composition of the PPI population, will be made prior to the freezing of the database and will be documented in a separate memo.

#### Table 3-5

#### Acceptable Day Ranges for Vaccination Visits

		Day Range for Inclusion		
Dose of 9-Valent HPV L1 VLP	Protocol Specified	in Statistical Analysis		
Vaccine Scheduled for Injection	Visit Window	(Relative to Day $1^{\dagger}$ )		
Dose 1	Day 1 †	0		
Dose 2	Month $2 \pm 3$ weeks	36 to 84		
Dose 3	Month $6 \pm 4$ weeks	148 to 218		
† Day 1 refers to the date when dose 1 of 9-valent HPV L1 VLP vaccine is injected. For				
post-Day 1 vaccinations, the day ranges for inclusion in the statistical analysis are wider				
than the protocol specified visit windows primarily to account for differences at the sites				
in counting months (e.g., 1 calendar month versus 30 days versus 4 weeks).				

#### Table 3-6

#### Acceptable Day Ranges for Collection of Serum Samples

Study Visit	Sample Type	Target Collection Day (Relative to Day 1 † )	Day Range for Inclusion in Statistical Analysis †	
Day 1	Serum	0	-14 to 0 (Relative to Day 1)	
Month 7	Serum	30 days post dose 3	21 to 49 post dose 3	
Month 12	Serum	365	274 to 547	
Month 24	Serum	730	548 to 914	
Month 36	Serum	1096	915 to 1552	
Month 66	Serum	2009	1553 to 2374	
Month 90	Serum	2739	2375 to 3287	
Month	Serum	3835	3288 to 4384	
126				
† Day 1 refers to the date when dose 1 of 9-valent HPV L1 VLP vaccine is				
injected. For Month 7, indicated target collection/day range is relative to				
date of injection of dose 3 of 9-valent HPV L1 VLP vaccine.				

#### **3.5.4.2 Safety Analysis Populations**

All subjects who received at least 1 study vaccination and have follow-up data will be included in the safety summaries.

76

#### **3.5.4.3 Effectiveness Analysis Populations**

Assessment of effectiveness will be conducted on two analysis populations: the perprotocol effectiveness (PPE) and the full analysis set (FAS) populations. The primary analysis will be conducted on the PPE population. The two analysis populations differ as described below with regard to compliance to vaccination regimen and potential HPV infection status at the time of vaccination of 9-valent HPV L1 VLP vaccine.

#### Per-Protocol Effectiveness (PPE)

The PPE analysis population is HPV type-specific. In analyses of endpoints related to a specific HPV type (e.g., HPV 16-related endpoints) the PPE population-eligible subjects include those who:

- (1) received 3 doses of 9-valent HPV L1 VLP vaccine within 1 year; AND
- (2) were seronegative by cLIA to the specific HPV type at the time of injection of dose 1 of 9-valent HPV L1 VLP vaccine (seronegative to both types 6 and 11 in analysis of HPV 6-related, and HPV 11-related endpoints); AND
- (3) Have no other protocol violations that could interfere with the evaluation of the effectiveness of the study vaccine. Specifically, at base study Day 1, satisfied inclusion criterion 5 (i.e., " Subject must not yet have had coitarche and does not plan on becoming sexually active during the Day 1 through Month 7 period.") specified in Section 2.2 of the protocol of the base study (i.e., Protocol V503-002-00).

Inclusion criterion 5, at base study, was intended to capture subjects who had not yet been infected with HPV through sexual intercourse and were therefore likely to be HPV-naïve during the period of vaccination with 9-valent HPV L1 VLP vaccine. The seronegativity condition is another criterion intended to capture subjects who were still HPV-naïve during the period of vaccination of 9-valent HPV L1 VLP vaccine

Note that a subject can be both PPE population-eligible for analyses of endpoints related to one HPV type (e.g., HPV 16-related endpoints) and PPE population-ineligible for analyses of endpoints related to another HPV type (e.g., HPV 18-related endpoints).

In analyses of endpoints related to any vaccine HPV type (e.g., HPV 6/11/16/18/31/33/45/52/58-related endpoints), the PPE population-eligible subjects include those who are PPE population-eligible for *any of* the HPV types 6, 11, 16, 18, 31, 33, 45, 52, or 58.

Only PPE population-eligible subjects who are at least 16 years of age and have at least one follow-up visit with PCR data will contribute to the PPE analyses.

The aforementioned definition of the PPE analysis population applies to HPV types 6, 11, 16, 18, 31, 33, 45, 52, and 58 only. There is no available serostatus information at the time of injection of dose 1 of 9-valent HPV L1 VLP vaccine with respect to non-vaccine HPV types (35, 39, 51, 56, and 59). In the absence of serostatus or DNA status with respect to non-vaccine HPV types at the time of injection of dose 1 of 9-valent HPV L1 VLP vaccine a PPE analysis population will not be defined for analyses of non-vaccine HPV types will be conducted in the full analysis set and in addition in a population that satisfies all conditions but one of the PPE, namely the seronegativity condition (2)

